^m Blood samples for biomarkers will be collected 2 times prior to receiving the first dose (collect once during Screening and then again at Day 1 pre-dose, the 2 collections should be at least 2 weeks apart). Collection of blood (for serum, citrated and K2-EDTA, or P100 plasma) and urine.

ⁿ In case of any suspected case of hypersensitivity or anaphylaxis additional samples for the assessment of ADA may be collected at or near the time of the event.

^o If a VOC crisis occurs, samples will be collected as per unscheduled visit.

^p The patient will record symptoms of VOC in a paper diary throughout the study. The Investigator or qualified designee will review the patient diary at every visit.

^q The Investigator or qualified designee will meet with the participant at each visit to ensure they carry the clinical study participant safety card at all times and to review the potential meningococcal infection risks of ALXN1820, and to address any safety concerns of the participant.

^r Collection of adverse events and serious adverse events will begin after ICF signing.

Table 7: Schedule of Activities – Screening Through Day 43 (Optional Cohort 3) – Q2W Dosing

Abbreviations: ADA = antidrug antibody; BMI = body mass index; CAP = complement alternative pathway; ECG = electrocardiogram; HiB = *Haemophilus influenzae* type B; HIV = human immunodeficiency virus; ICF = informed consent form; IEC = Independent Ethics Committee; K2-EDTA = dipotassium ethylenediaminetetraacetic acid; MCV4 = tetravalent meningococcal conjugate vaccine; NA = not applicable; PD = pharmacodynamic(s); PK = pharmacokinetic(s); Q2W = every 2 weeks; VOC = vaso-occlusive crisis.

Table 8: Schedule of Activities – Day 57 Through End of Follow-up Period for Multiple Dose Follow-up (Optional Cohort 3)

Study Day	Day 57	Day 85 ^a	Day 113	Day 141 ^a	Day 169 /ET/ Unscheduled	Complement Activity Follow-up ^b
Window (Day)	± 3	± 3	± 3	± 3	± 3	±14
Physical examination					X	
Abbreviated physical examination	X		X			
Vital sign measurements	X		X		X	
Triplicate ECG	X		X		X	
Clinical chemistry ^c	X		X		X	
Hematology ^c	X		X		X	
Coagulation ^c	X		X		X	
Urinalysis	X		X		X	
Serum/urine pregnancy test	X		X		X	
PK samples	X		X		X	
Blood samples for PD panel (serum total and free properdin, CAP activity)	X		X		X	X
Biomarkers ^d	X		X		X	
Immunogenicity (ALXN1820 ADA) ^e			X		X	
Assessment of VOC ^{f,g}	←Monitor continuously→					
Review patient diary ^g	X	X	X	X	X	X
Review safety card ^h	X	X	X	X	X	X
Concomitant medications	←Monitor continuously→					
Adverse events ⁱ	←Monitor continuously→					

^a Visit may be performed remotely (phone or video calls).

^b If CAP activity has not returned to a normal range or 80% of the baseline level at the end of the Follow-up Period, patients may have additional Follow-up Visits every 12 weeks until CAP activity has been confirmed to either have returned to a normal range or 80% of the baseline level. This visit may be completed at home.

Table 8: Schedule of Activities – Day 57 Through End of Follow-up Period for Multiple Dose Follow-up (Optional Cohort 3)

^c Non-fasting blood samples will be obtained.

^d Collection of blood (for serum, citrated and K2-EDTA, or Plasma P100 plasma) and urine.

^e In case of any suspected case of hypersensitivity or anaphylaxis additional samples for the assessment of ADA may be collected at or near the time of the event.

^f Assessment of VOC must be performed by a healthcare provider.

^g The patient will record symptoms of VOC in a paper diary throughout the study. The Investigator or qualified designee will review the patient diary at every visit.

^h The Investigator or qualified designee will meet with the participant at each visit to ensure they carry the clinical trial participant safety card at all times and to review the potential meningococcal infection risks of ALXN1820, and to address any safety concerns on the part of the participant.

ⁱ Collection of adverse events and serious adverse events will begin after ICF signing.

Abbreviations: ADA = antidrug antibody; CAP: complement alternative pathway; ECG = electrocardiogram; ET = early termination; ICF = informed consent form; K2-EDTA = dipotassium ethylenediaminetetraacetic acid; PD = pharmacodynamic(s); PK = pharmacokinetic(s); VOC = vaso-occlusive crisis.

2. INTRODUCTION

2.1. Study Rationale

ALXN1820 (anti-properdin/anti-serum albumin bispecific VHH antibody) is a novel properdin blocking agent being developed for the treatment of diseases involving dysregulated CAP activity. The ALXN1820 molecule is bispecific, comprising a VHH antibody domain that binds and blocks properdin connected via a linker to a VHH domain that binds serum albumin, thereby conferring an extended circulatory half-life to the molecule.

ALXN1820 binds to properdin with a high affinity to prevent stabilization of the CAP complement component C3 (C3) and complement component C5 (C5) convertases that cleave C3 and C5 into their activation products. Quantitative blockade of properdin has been shown to be safe in human based on experience with the properdin binding antibody ALXN1510 (see Section 4.3). ALXN1820 is currently being evaluated in an ongoing Phase 1 study in healthy adult participants (Study ALXN1820-HV-101), and doses and dosing regimens for participants in this study were determined using cumulative safety data and an interim PK/PD analysis from participants enrolled in the ongoing Phase 1 study as well as data from the 6-month GLP toxicology in monkeys.

The purpose of this study in patients with SCD is to evaluate the safety, tolerability, efficacy, PK, PD, and immunogenicity of multiple doses and dosing regimens of ALXN1820 administered subcutaneously (ALXN1820 SC).

The study will include up to 3 cohorts with multiple SC doses and dosing regimens of open-label ALXN1820 in adult patients with SCD. Data from this study are anticipated to help design future studies in patients with SCD and other complement-mediated diseases.

2.2. Background

A detailed description of the chemistry, pharmacology, and toxicology data available for ALXN1820 is provided in the Investigator's Brochure (IB).

2.2.1. Chemistry

ALXN1820 is a recombinant, humanized VHH bispecific antibody that binds to human properdin and serum albumin. The antibody consists of a single polypeptide chain of 256 amino acids, which is comprised of an anti-albumin domain at the N-terminus that is fused to a C-terminal anti-properdin domain via a 15 amino acid linker. The variable region domains that form the serum albumin and properdin binding sites consist of llama complementarity determining regions grafted into human germline frameworks. Within the framework regions, llama residues at 11 positions were left unchanged to maintain antigen binding, aqueous solubility, and overall stability. There are 2 intrachain disulfide bonds, 1 disulfide bond localized in each VHH domain. The theoretical average molecular mass of the antibody is 27,350.2 Da. At pH 7.4, ALXN1820 exhibited a binding dissociation constant (K_D) of 323 pM for human properdin and K_D of 439 pM for human serum albumin. The IC_{50} for blockade of human CAP hemolysis by ALXN1820 (20% v/v final serum) was 29 nM. ALXN1820 blocked C3 fragment, properdin and complement component C9 (C9) deposition onto a myeloperoxidase substrate by

human serum (20%v/v) with IC₅₀ values of approximately 20 nM (C3), 15 nM (properdin) and 19 nM (C9).

2.2.2. Nonclinical Pharmacology

In a study of the potency of blockade of in vitro CAP hemolysis by ALXN1820 using sera across a range of species, significant species cross reactivity was observed only when using sera from cynomolgus and rhesus macaque. CAP hemolytic activities in the sera of mouse, rat, guinea pig, minipig, beagle and rabbit were not inhibited by the highest concentration of ALXN1820 examined (> 100 µg/mL). The IC₅₀ for blockade of cynomolgus CAP hemolysis by ALXN1820 (20% v/v final serum) was 47 nM. ALXN1820 exhibited a binding K_D of 2.9 nM for cynomolgus properdin and K_D of 2.1 nM for cynomolgus serum albumin. ALXN1820 blocked C3 fragment, properdin and C9 deposition onto a myeloperoxidase substrate by cynomolgus monkey serum (20%v/v) with IC₅₀ values of approximately 11 nM (C3), 9 nM (properdin) and 17 nM (C9). The lack of species cross reactivity beyond primates described above prevented testing the biologic activity of ALXN1820 in traditional rodent models of diseases involving dysregulated complement activity. Collectively therefore, the nonclinical in vitro and in vivo studies to assess the pharmacologic, PK, PD and toxicologic properties of ALXN1820 are being performed in cynomolgus monkeys.

2.2.3. Toxicology

Nonclinical safety profile of ALXN1820 has been evaluated in an in vitro GLP tissue cross reactivity (TCR) study and in both a non-GLP and GLP in vivo studies in cynomolgus monkeys. In GLP toxicology studies ALXN1820 was administered by intravenous (IV) administration (up to single dose of 100 mg/kg) and SC administration (up to 26 weekly doses of 300 mg/kg/week). ALXN1820 did not demonstrate any non-specific binding to human tissues in the TCR study. Based on the absence of any adverse systemic or local toxicity in cynomolgus monkeys, 300 mg/kg/week was considered the no observed adverse effect level (NOAEL) for SC administration and 100 mg/kg was considered as the NOAEL for IV administration of ALXN1820. Systemic exposures (maximum observed serum concentration [C_{max}] and area under the concentration-time curve from time 0 to 168 hours [AUC₀₋₁₆₈] of 8,570 µg/mL and 1,160,000 µg·hr/mL, respectively), after the last dose at the NOAEL in the SC group, yielded exposure multiples of ~30-fold to the projected exposures at the anticipated human dose of 300 mg QW. Antidrug antibodies, when observed in a very small number of monkeys, did not have any impact on systemic exposure or toxicity profile.

2.3. Benefit/Risk Assessment

There may be potential benefits to patients with SCD (See Section 2.3.2).

Identified and potential risks are described below. More detailed information about the known and expected benefits and risks and reasonably expected AEs of ALXN1820 may be found in the IB. Potential risk mitigation strategies are described in Table 9.

2.3.1. Risk Assessment

Besides the first-in-human (FIH) Phase 1 Study ALXN1820-HV-101 in healthy participants, this study is the second human exposure to ALXN1820 and the first exposure to patients with SCD.

As there is limited clinical experience to date, the potential risks are based on the class of the molecule and its mechanism of action. No potential risks were identified from the repeat dose toxicity study in cynomolgus monkeys with ALXN1820 after 26 weekly SC doses up to 300 mg/kg/week or after a single IV dose up to 100 mg/kg and no safety concerns in healthy participants have been identified as of 11 Mar 2022 after 5 weekly SC doses up to 150 mg or after a single SC dose of 1200 mg.

2.3.1.1. *Neisseria meningitidis* Infections

Increased susceptibility to infection with *Neisseria meningitidis* is a known risk associated with properdin deficiency and has been well described with properdin-deficient patients (Figueroa, 1991). Similar to properdin deficiency, the main risk associated with the use of ALXN1820 (properdin inhibitor) is expected to be the risk of meningococcal infections. Specific risk mitigation measures are in place to address this risk.

Clinically, the risk of *N. meningitidis* is mitigated in patients with properdin deficiency by vaccinating all patients against *N. meningitidis* with tetravalent meningococcal conjugate vaccine (MCV4) and serogroup B vaccines before dosing.

Patients will be vaccinated with MCV4 and serogroup B meningococcal vaccinations at least 14 days before dosing, if not already vaccinated within 3 years before the first dose (or per national/local guidelines). Participants who initiate study intervention treatment less than 14 days after receiving a meningococcal vaccine must receive treatment with appropriate prophylactic antibiotics until at least 2 weeks after vaccination. Every effort should be made to start the meningococcal vaccination series at least 14 days prior to randomization.

Additionally, participants may be treated with prophylactic antibiotics at the Investigator's discretion.

2.3.1.2. Immunogenicity and Hypersensitivity

ALXN1820 has the potential to be immunogenic and may be associated with hypersensitivity reactions. Some healthy participants are also known to have pre-existing antibody to VHH antibodies. Antibodies to ALXN1820 have been observed in 14 of 100 healthy participant serum samples tested in an in vitro screening assay.

Monitoring of immunogenicity for ALXN1820 is in place for this study as specified in the SoA (Section 1.3).

Table 9: Potential Risks and Mitigation Strategies

Potential Risk of Clinical Significance	Summary of Data/Rationale for Risk	Mitigation Strategy
Treatment with ALXN1820		
Meningococcal infection	ALXN 1820 blocks properdin which can result in increased susceptibility to Neisseria meningitidis , likely with fulminant clinical manifestations.	
Participants must be vaccinated against all available serotypes of N. meningitidis (A, C, Y, W 135, and B). However, vaccination may not be sufficient to prevent meningococcal infection.
 
Prophylactic antibiotics will be used at the investigator's discretion. Timing for meningococcal vaccinations can be mandated per local/national guidelines.
 
(See Sections 1.3, 2.3.1.1 and 8.2.9)
 
Participants will be provided a safety card to carry at all times and for 5 months after the final dose of ALXN1820.

Immunogenicity	Treatment with any therapeutic protein may induce an immune response. Occasionally, this immune response is clinically meaningful. The consequences of an immune reaction to a therapeutic protein range from transient appearance of antibodies, without any clinical consequence, to severe, life-threatening conditions. Potential clinical consequences also may include severe hypersensitivity-type reactions, decrease in efficacy and induction of autoimmunity.	Algorithm for hypersensitivity reaction management; Stopping rules and staggered dosing

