4. STUDY DESIGN

4.1. Overall Design

This is a Phase 2a study, with up to 3 multiple dose cohorts of open-label ALXN1820 SC in adult patients with SCD (HbSS and HbS β^0 -thalassemia).

The study will be conducted in up to 30 adult patients with SCD enrolled in up to 3 open-label cohorts (Cohorts 1, 2 and 3 [optional]) to receive multiple SC doses of open-label ALXN1820. ALXN1820 will be administered as described in Table 11.

Table 11: ALXN1820-SCD-201 Dosing Cohorts

Cohort	N	Study Drug	Route of Administration	Planned Dose	Number of Doses/Dose Interval
1	Up to 12 maximum of 6 on stable dose of hydroxyurea	ALXN1820	SC	300 mg	QW \times 13
2	Up to 12 maximum of 6 on stable dose of hydroxyurea	ALXN1820	SC	600 mg	Q4W \times 4
3 (optional)	Up to 6 maximum of 3 on stable dose of hydroxyurea	ALXN1820	SC	300 mg	Q2W \times 4

Abbreviations: N = number of participants; QW = once weekly; Q2W = once every 2 weeks; Q4W = once every 4 weeks; SC = subcutaneous.

The dose and dosing intervals for Cohorts 1 and 2 were determined using cumulative safety data, an interim PK/PD analysis from participants enrolled in Study ALXN1820-HV-101, and data from the 6-month GLP toxicology study in monkeys. Optional Cohort 3 will be initiated after evaluation of safety and PK/PD data from Cohorts 1 and 2.

Cohort 1 and Cohort 2 will run in parallel, and patients will be randomized 1:1 to either of the cohorts on determination of eligibility. The decision to initiate Optional Cohort 3 will be made at Alexion's discretion and will be based on analysis of PK/PD and safety after at least 8 patients from Cohorts 1 and 2 (4 from each cohort) have enrolled. Furthermore, enrollment of Optional Cohort 3 will start after Cohorts 1 and 2 are fully enrolled. Each cohort will be stratified to ensure patients with SCD who are treated with a stable dose of hydroxyurea and patients with SCD who are not currently treated with hydroxyurea are included. For patients who were previously treated with hydroxyurea but are not currently on hydroxyurea, treatment must be stopped at least 30 days prior to providing informed consent.

This study will use an independent DMC to monitor safety and to perform the planned interim analyses of the study. At Alexion's discretion, and after consultation with the DMC, additional

participants with SCD may be enrolled as replacement participants if a participant discontinues during the Dosing Period for reasons other than drug related AEs.

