6.6. Dose Modification

Decisions to continue or modify dosing will be made by the Investigator and/or DMC after review of the safety data. The DMC may also make recommendations regarding safety issues, study conduct, or study suspension.

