7.2. Stopping Criteria

7.2.1. Individual Stopping Rules

Participants should be considered for discontinuation from intervention if any of the following occur during the study:

- Serious hypersensitivity reaction;
- Grade 3 or higher injection site reactions;
- Severe uncontrolled infection;
- Serious *N meningitidis*, *S pneumoniae*, or *H influenzae* infections;
- Use of disallowed medication as defined in Section 6.5.2;
- Pregnancy or planned pregnancy; or
- Any AE, laboratory abnormality, or intercurrent illness which, in the judgment of the Investigator or Alexion, presents a substantial clinical risk to the patient with continued study drug dosing.

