7.2.2. Study Stopping Rules

The study may be terminated at the recommendation of the DMC, if the following occur and are deemed to be related to the study drug:

- Two or more meningococcal infections;
- Two or more serious (\geq Grade 3) pneumococcal infections;
- Two or more serious (\geq Grade 3) *H influenzae* infections;
- One meningococcal, pneumococcal, or *H influenzae* infection resulting in a fatal outcome.

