9.6. Data Monitoring Committee

An independent DMC, comprising experts in relevant fields with no direct relationship to the study, will be appointed by Alexion. The specific responsibilities of the DMC and a schedule of meetings will be described in the DMC Charter.

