10.1.9. Study and Site Start and Closure

The study start date is the date on which the first participant is consented.

Alexion reserves the right to close the study site or terminate the study at any time for any reason at its sole discretion. Study sites will be closed after the study is completed or following the decision to close or terminate the study. A study site is considered closed when all participants have completed the last study visit or Early Discontinuation Visit, all data have been collected and entered into the electronic data capture system, all required documents and study supplies have been collected and reconciled, and a study-site closure visit has been performed.

The Investigator may initiate study-site closure at any time, provided there is reasonable cause and sufficient notice is given in advance of the intended termination.

Reasons for the early closure of a study site by Alexion or Investigator may include but are not limited to:

- Failure of the Investigator to comply with the protocol, the requirements of the IRB/IEC or local health authorities, Alexion's procedures, or ICH GCP guidelines
- Inadequate recruitment of participants by the Investigator
- Discontinuation of further study intervention development

Alexion or health authority may terminate the study for reasonable cause. Conditions that may warrant termination of the study include, but are not limited to:

Discovery of an unexpected, serious, or unacceptable risk of the study intervention to participants enrolled or continuing in the study

Alexion decision to suspend or discontinue testing, evaluation, or development of the study intervention

If the study is prematurely terminated or suspended, Alexion shall promptly inform the Investigators, IRBs/IECs, regulatory authorities, and any contract research organization(s) used in the study of the reason for termination or suspension, as specified by the applicable regulatory requirements. The Investigator shall promptly inform the participant and should assure appropriate participant therapy and/or follow-up.

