10.6. Management of Potential Adverse Events During Study Drug Administration

Injection-associated reactions are a potential risk with the use of therapeutic protein products; these reactions can be nonimmune or immune mediated (eg, hypersensitivity reactions). Signs and symptoms may include headache, fever, facial flushing, pruritus, myalgia, nausea, chest tightness, dyspnea, vomiting, erythema, abdominal discomfort, diaphoresis, shivers, hypertension, lightheadedness, hypotension, palpitations, and somnolence. Signs and symptoms of hypersensitivity or allergic reactions may include hives, swollen face, eyelids, lips, or tongue, or trouble with breathing.

All injection-associated reactions will be reported to the Investigator and qualified designee. The Investigator and qualified designee are responsible for detecting, documenting, and recording events that meet the definition of AE or SAE and remain responsible for following up events that are serious, considered related to the study drug or study procedures, or that caused the participant to discontinue ALXN1820.

Definitions and procedures for recording, evaluating, follow-up, and reporting AEs and SAEs are outlined in Section 10.3.

Before study drug administration, the treating physician and other appropriate personnel must make certain that medication (ie, adrenaline, inhaled beta agonists, antihistamines, corticosteroids) and other equipment to treat anaphylaxis are readily available. Alexion must be notified within 24 hours of any injection site reaction requiring interruption or discontinuation of study drug. Participants who experience a reaction during the administration of study drug should be treated according to institutional guidelines.

Participants who experience a severe reaction during administration of study drug resulting in discontinuation of study drug should undergo all scheduled safety, PK, and PD evaluations required by the protocol, if possible.

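### Table 9 credits staggered dosing that the protocol does not describe; no study-level stopping trigger covers hypersensitivity, and scheduled ADA sampling has a 56-day on-treatment gap

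*Protocol*

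**What the plan says.** Protocol Section 2.3.1.2, Table 9, recognises that an immune response to the drug can range up to life-threatening conditions and severe hypersensitivity-type reactions. The mitigation listed is "Algorithm for hypersensitivity reaction management; Stopping rules and staggered dosing". The same section refers to the schedule of activities for immunogenicity monitoring.

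On the start of dosing, Section 4.1 says "Cohort 1 and Cohort 2 will run in parallel, and patients will be randomized 1:1 to either of the cohorts on determination of eligibility". Optional Cohort 3 follows only after safety and PK/PD data from Cohorts 1 and 2 have been evaluated and those cohorts are full.

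On stopping, Section 7.2.1 opens with "Participants should be considered for discontinuation from intervention if any of the following occur during the study" and lists serious hypersensitivity first. Section 7.2.2 says that the study may be terminated on the DMC's recommendation "if the following occur and are deemed to be related to the study drug", and then gives four triggers.

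On ADA, Tables 3 and 4 schedule samples on Days 1, 15, 29 and 85, and Table 6 adds Days 155 and 211. Footnotes permit, but do not require, extra samples near a suspected hypersensitivity or anaphylaxis event. SAP Section 4.3.3 classifies ADA responses and follows titer over time.

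**The concern.** Safety is the primary objective, and the benefit/risk section credits the design with a safeguard that no other section describes. The risk is not remote on the protocol's own account: Section 2.3.1.2 reports antibodies to the drug in 14 of 100 healthy-participant samples in an in vitro screening assay.

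Two practical matters follow. After a drug-related anaphylaxis in one patient, nothing in the protocol text says whether other patients may receive a first dose before the DMC has looked at the event. And between Days 29 and 85, if drug concentration falls or CAP activity returns, there is no scheduled ADA result beside the PK and PD values to show whether antibody is the cause. A short-lived antibody response in that interval could also pass unrecorded.

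**Working it through.** The plan states no figure of its own on this point. The check sets the sections side by side and counts from the schedules.

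**Staggering.** Sections 1.1, 1.2, 4.1 and 6.3 were compared with Table 9. None gives a sentinel patient, a minimum interval between first doses or a pause within a cohort. The later start of Cohort 3 puts an optional cohort in sequence; it does not space out the first patients exposed.

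**Stopping rules.**
- Individual level (7.2.1): serious hypersensitivity is named. The general rule on any AE posing substantial clinical risk would cover it as well. The rules ask that discontinuation be considered; they do not mandate it.
- Study level (7.2.2): the four triggers are two or more meningococcal infections; two or more serious pneumococcal infections; two or more serious *H influenzae* infections; and one fatal infection with any of the three. Triggers for hypersensitivity, anaphylaxis or ADA: 0 of 4.

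**ADA gaps in Cohorts 1 and 2** (days from Tables 3, 4 and 6):
- 15 − 1 = 14; 29 − 15 = 14; 85 − 29 = 56; then, after the last dose on Day 85, 155 − 85 = 70 and 211 − 155 = 56.
- The longest on-treatment gap is 56 days. Visit windows make it 54 to 58 days in Cohort 1 (±1 day at each end) and 50 to 62 days in Cohort 2 (±3 days at each end).

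**Doses strictly inside the gap.**
- Cohort 1 (weekly, Days 1 to 85, 13 doses): Days 36, 43, 50, 57, 64, 71 and 78, which is 7 doses, or 7 × 300 = 2100 mg of 13 × 300 = 3900 mg (54%).
- Cohort 2 (Days 1, 29, 57, 85): Day 57, which is 1 dose, or 600 mg of 4 × 600 = 2400 mg (25%).
- The tables do not say whether ADA is drawn before the dose. If it is, the Day 29 dose also falls in the gap, giving 8 and 2 doses.

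**Pairing with PK and PD.** On-treatment PK/PD days are 1, 15, 29, 43, 57, 71 and 85. ADA is drawn on 4 of these 7; Days 43, 57 and 71 have none.

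**With a Day 57 sample.** 57 − 29 = 28 and 85 − 57 = 28, so the longest on-treatment gap falls from 56 to 28 days. Cohort 1 doses strictly between samples fall from 7 to 3 in each interval (Days 36, 43, 50 and Days 64, 71, 78). Paired PK/ADA days rise from 4 of 7 to 5 of 7.

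**The case against.** The strongest reply is that Table 9 promises stopping rules, not study-level ones, and 7.2.1 supplies one. That stands: the stopping-rule half of the entry is met for individuals.

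A reader might go further and infer that a serious reaction would meet no study-level response. The documents do not support that. Section 2.3.3 has the DMC evaluating data at prespecified times and advising on dose modification or termination. Section 6.6 adds "The DMC may also make recommendations regarding safety issues, study conduct, or study suspension". Section 10.1.9 lists as grounds for termination "Discovery of an unexpected, serious, or unacceptable risk of the study intervention to participants enrolled or continuing in the study". Section 10.6 requires that medication and "equipment to treat anaphylaxis are readily available" before dosing, Section 8 asks for immediate discussion of safety concerns with the sponsor, and SAEs must be reported within 24 hours (8.3.1, 10.3.4). Section 9.6 adds that "The specific responsibilities of the DMC and a schedule of meetings will be described in the DMC Charter"; the charter is not among the documents and may define a review or pause. What remains is that the protocol text itself defines no such trigger.

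It can also be said that acting on one event is stricter than 7.2.2, which needs two non-fatal meningococcal infections. But those rules concern termination. A trigger for review with a temporary hold on first doses is a lesser step.

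On ADA, a reader might infer that the SAP categories cannot be assigned without more samples, or that the gap itself leaves patients unprotected. Neither holds. The categories in SAP 4.3.3 use baseline and any post-dose result, so the existing samples suffice; a response that lasts to Day 85 still counts toward incidence. No dosing rule depends on ADA, and AEs, vital signs, injection sites, PK and PD are followed throughout. An extra sample would not by itself prevent a reaction.

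**Conclusion.** The point holds in a limited form. Table 9 credits staggered dosing that the protocol does not describe. None of the four study-level triggers addresses hypersensitivity, although the individual rule and general powers exist. Scheduled ADA sampling leaves a 56-day on-treatment gap, with 7 Cohort 1 doses and 1 Cohort 2 dose strictly inside it and three PK/PD visits unpaired.

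The benefit of a further ADA sample is modest: narrower dating of onset, some short transient responses caught, and better interpretation of PK/PD changes. The documents give no onset or duration of antibody response, so the number of extra responses caught cannot be estimated from them.

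The gap counts scheduled samples only and refers to the protocol as planned. SAP Sections 1 and 1.2 report early termination with 2 patients enrolled and data listed only, so the practical effect on this trial is small. No sample size or error rate is affected. The change is worth making because it is cheap; correcting Table 9 alone would be close to clerical.

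**What to change.** (a) Add to Section 7.2.2 that a related anaphylaxis or serious hypersensitivity reaction triggers prompt DMC review, with no new first doses until that review is done. Cost: a possible short pause in enrolment. Patients already on treatment stay under 7.2.1.

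(b) Add an ADA sample on Day 57 in Tables 3 and 4. Cost: one extra assay per patient, 24 for the planned 24 patients, taking scheduled ADA samples through Day 211 from 6 to 7. The visit already draws PK and PD blood, and Section 8.5 allows PK samples to be used for safety or efficacy questions, so the existing draw may be enough.

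(c) Delete staggered dosing from Table 9 or, if the sponsor intends it, describe it in Section 4.1. Cost: a one-line edit, or a short added paragraph.
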